4. SUBJECT REGISTRATION

All subjects must be registered through the Hoosier Cancer Research Network (HCRN) electronic data capture (EDC) system. A subject is considered registered when an “On Study” date is entered into the EDC system. Subjects must be registered after signing consent but prior to starting protocol therapy.

5. TREATMENT PLAN

5.1. Overall Design and Study Plan

The primary objective of this open label, non-randomized Phase II trial is to determine the activity of nivolumab in combination with ramucirumab in subjects with histologically-confirmed malignant mesothelioma not amenable to curative surgery and who have received at least one pemetrexed-containing chemotherapy regimen. The primary endpoint in this study is response rate (RR). Nivolumab and ramucirumab will be given on Day 1 of each 14-day cycle. Treatment will continue for up to 24 months (52 cycles) or until disease progression by RECIST 1.1 criteria, unacceptable toxicity, subject refusal, or subject death. Subjects who voluntarily stop the study, have progressive disease, or unacceptable toxicities will be followed for a total of 24 months after initiation of study treatment.

Correlative research analyses include examining the relationship between best clinical response overall with tissue PD-L1, and at the end of Cycle 4 (Week 8) with changes in soluble PD-L1, cytokine genes expressions and number of CD8+ and Granzyme B+ T cells in tumor tissue from before therapy to the end of Cycle 4 (Week 8). Research analyses also include examining the relationship between changes in soluble PD-L1 level, during therapy (assessed pre-dose Cycles 1 and 5 [Days 1 and 57 of treatment period, respectively]) with best clinical response (modified RECIST 1.1 criteria) at the end of Cycle 4 (Week 8).

5.2. Pre-medication

No premedication is indicated for nivolumab. However, for subjects who experience a Grade 1 or Grade 2 infusion reaction, prior to subsequent infusions it is recommended that diphenhydramine 50 mg (or equivalent) and/or paracetamol (acetaminophen) 325 to 1000 mg should be administered at least 30 minutes before additional nivolumab administrations. If necessary, corticosteroids (recommended dose: up to 25 mg of IV hydrocortisone or equivalent) may be used.

Prior to ramucirumab infusion, IV diphenhydramine (or equivalent) will be given. For subjects who experience a Grade 1 or Grade 2 infusion-related reaction (IRR), premedication must be given for all subsequent infusions. If a subject has a second Grade 1 or Grade 2 IRR, administer dexamethasone 10 mg (or equivalent); for subsequent infusions, premedicate with the following (or equivalent): diphenhydramine hydrochloride (IV), acetaminophen, and dexamethasone.

5.3. Drug Administration

Drug	Dose	Length and route of administration	Frequency of administration	Length of cycle
Nivolumab (1 st)	240 mg	30 min (-5/+10), IV	Day 1	14 days
Ramucirumab (2 nd)	8 mg/kg	60 min (-5, +10), IV	Day 1	

NOTE: Infusions may be given \pm 3 days for reasons such as observed holidays, inclement weather, scheduling conflicts, etc. It should be clearly documented in subject's chart and case report forms. **NOTE:** there must be at least 12 days between each dose of nivolumab.

5.3.1. Sequencing of Nivolumab + Ramucirumab Administration

Dosing will occur in 2-week cycles. On Day 1 of each cycle, the nivolumab intravenous infusion is given first followed 60 minutes after the end of the infusion (first two cycles) or 15-30* minutes after the end of the infusion (subsequent cycles) by the ramucirumab infusion.

*The interval between infusions for subsequent cycles beyond Cycle 2 will be shortened to 15-30 minutes provided that subjects in the first two cycles show no untoward effects from nivolumab which would require a 60-minute observation period.

5.3.2. Nivolumab Dose and Administration

Nivolumab will be administered as a 30-minute intravenous infusion dosed at 240 mg. Nivolumab is to be administered as an IV infusion through a 0.2-micron to 1.2-micron pore size, low-protein binding polyethersulfone membrane in-line filter. It is not to be administered as an IV push or bolus injection. Nivolumab injection can be infused undiluted (10 mg/mL) or diluted with 0.9% Sodium Chloride Injection, USP or 5% Dextrose Injection, USP to protein concentrations as low as 1 mg/mL. Care must be taken to assure sterility of the prepared solution as the product does not contain any antimicrobial preservative or bacteriostatic agent.

5.3.3. Ramucirumab Dose and Administration

Ramucirumab will be administered as a 60-minute intravenous infusion dosed at 8 mg/kg.

The dosing calculations should be based on the actual body weight at baseline. If the subject's weight on the day of dosing differs by > 10% from the weight used to calculate the original dose, the dose must be recalculated. All doses should be rounded to the nearest milligram. There will be no dose modifications allowed.

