5.4. Supportive Care

Subjects should receive appropriate supportive care measures as deemed necessary by the treating investigator. Suggested supportive care measures for the management of adverse events that are related to ramucirumab and nivolumab are outlined below. Where appropriate, these guidelines include the use of oral or intravenous treatment with corticosteroids as well as additional anti-inflammatory agents if symptoms do not improve with administration of corticosteroids. Note that several courses of steroid tapering may be necessary as symptoms may worsen when the steroid dose is decreased. For each disorder, attempts should be made to rule out other causes such as metastatic disease or bacterial or viral infection, which might require additional supportive care. The treatment guidelines are intended to be applied when the investigator determines the events to be related to ramucirumab or nivolumab.

5.4.1. Suggested supportive care measures for the management of adverse events that are related to ramucirumab

Infusion-Related Reactions

- Signs and symptoms usually develop during or shortly after drug infusion and generally resolve completely within 24 hours of completion of infusion.
- For guidelines on treatment holds, timing for restarting treatment or discontinuing treatment permanently, see Section 6.2.1, Table 2.

Proteinuria

- Treat proteinuria according to established guidelines.
- For guidelines on treatment holds, timing for restarting treatment or discontinuing treatment permanently, see Section 6.2.1, Table 2.

Hypertension

- Treat hypertension according to established guidelines.
- For guidelines on treatment holds, timing for restarting treatment or discontinuing treatment permanently, see Section 6.2.1, Table 2.

Wound Healing

- Treat wound according to established guidelines.
- For guidelines on treatment holds, timing for restarting treatment or discontinuing treatment permanently, see Section 6.2.1, Table 2.

Reversible Posterior Leukoencephalopathy Syndrome (RPLS)

- Treat RPLS according to established guidelines.
- For guidelines on treatment holds, timing for restarting treatment or discontinuing treatment permanently, see Section 6.2.1, Table 2.

Arterial Thrombotic Events

- Initiate anticoagulation therapy.
- For guidelines on treatment holds, timing for restarting treatment or discontinuing treatment permanently, see Section 6.2.1, Table 2.

Pulmonary Embolism (PE) or Venous thromboembolism (VTE)

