6.3 Dose Modifications

6.3.1 Ramucirumab Dose Modifications

Ramucirumab must be withheld for drug-related toxicities and severe or life-threatening AEs as per Table 2 below. See Section 5.4 for supportive care guidelines. **NOTE:** In addition to the guidelines below, subjects with intolerable or persistent Grade 2 drug-related AE may hold study medication at physician discretion.

Table 2: Ramucirumab dose modification guidelines for drug-related adverse events

Toxicity	Hold Treatment For	Timing for Restarting Treatment	Dose/rate reductions	Discontinue Subject
Proteinuria¹	urine protein levels $\geq 2\text{g}/24\text{hrs}$	once the urine protein level returns to $< 2\text{g}/24\text{hrs}$	Reduce dose to 6 mg/kg per dose for the first occurrence Reduce dose to 5 mg/kg for the second occurrence	For a third occurrence of $>2\text{g}/24\text{hrs}$, or if the protein level does not return to $<2\text{g}/24\text{hrs}$ within 2 weeks
	urine protein level $>3\text{g}/24\text{hrs}$ or in the setting of nephrotic syndrome	Permanently discontinue	Permanently discontinue	Permanently discontinue
Hypertension	Grade 3	Toxicity resolves to Grade 0-2 with medical management	No reduction if toxicity resolves	Permanently discontinue if medically significant hypertension cannot be controlled with antihypertensive therapy.
	Grade 4	Permanently discontinue	Permanently discontinue	Permanently discontinue
Wound healing complications	$\geq\text{Grade 1}$; (NOTE: interrupt drug prior to any scheduled surgery)	Restart when wound is fully healed	No dose reductions warranted	Wound does not heal: permanently discontinue
Reversible posterior leukoencephalopathy syndrome (RPLS)²	Any occurrence	Permanently discontinue	Permanently discontinue	Permanently discontinue
Arterial thrombotic events³	Grade 3 or more severe	Permanently discontinue	Permanently discontinue	Permanently discontinue
Pulmonary embolism (PE) or Venous thromboembolism (VTE)³	Any event that occurs OR worsens despite anticoagulation therapy	Permanently discontinue	Permanently discontinue	Permanently discontinue
Venous thromboembolism (Subjects with unresected primary)	Grade 3-4	When subject has begun anticoagulation	No dose reductions warranted	If in the opinion of the subject's physician, the tumor confers an

Toxicity	Hold Treatment For	Timing for Restarting Treatment	Dose/rate reductions	Discontinue Subject
tumors or local recurrence)³				excessive bleeding risk

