10.1.4 Dosage and Administration

Eli Lilly and Company will supply ramucirumab directly to sites at no cost to subjects in this clinical trial. Ramucirumab is supplied in a sterile form for intravenous use only. Ramucirumab is a sterile, preservative-free, clear to slightly opalescent and colorless to slightly yellow solution for intravenous infusion following dilution and preparation. Ramucirumab is supplied at a concentration of 10 mg/mL in either 100 mg (10 mL) or 500 mg (50 mL) single-dose vials. CYRAMZA is formulated in glycine (9.98 mg/mL), histidine (0.65 mg/mL), histidine

monohydrochloride (1.22 mg/mL), polysorbate 80 (0.1 mg/mL), sodium chloride (4.383 mg/mL), and Water for Injection, USP, pH 6.0.

Inspect vial contents for particulate matter and discoloration prior to dilution. Discard the vial, if particulate matter or discolorations are identified. Store vials in a refrigerator at 2°C to 8°C (36°F to 46°F) until time of use. Keep the vial in the outer carton in order to protect from light.

- Calculate the dose and the required volume of ramucirumab needed to prepare the infusion solution. The dosing calculations should be based on the actual body weight at baseline. If the subject's weight on the day of dosing differs by > 10% from the weight used to calculate the original dose, the dose must be recalculated. All doses should be rounded to the nearest milligram. Vials contain either 100 mg/10 mL or 500 mg/50 mL at a concentration of 10 mg/mL solution of ramucirumab.
 - Withdraw the required volume of ramucirumab and further dilute with only 0.9% Sodium Chloride Injection in an intravenous infusion container to a final volume of 250 mL. Do not use dextrose containing solutions.
 - Gently invert the container to ensure adequate mixing.
 - DO NOT FREEZE OR SHAKE the infusion solution. DO NOT dilute with other solutions or co-infuse with other electrolytes or medications.
 - Store diluted infusion for no more than 24 hours at 2°C to 8°C (36°F to 46°F) or 4 hours at room temperature (below 25°C [77°F]).
 - Discard vial with any unused portion of ramucirumab.

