11.1.3 Serious Adverse Event (SAE)

An SAE is an adverse event that:

- Results in death. **NOTE:** Death due to disease progression should not be reported as a SAE, unless it is attributable by the site investigator to the study drug(s)
- Is life-threatening (defined as an event in which the subject was at risk of death at the time of the event; it does not refer to an event which hypothetically might have caused death if it were more severe)
- Requires inpatient hospitalization for >24 hours or prolongation of existing hospitalization. **NOTE:** Hospitalization for anticipated or protocol specified procedures such as administration of chemotherapy, central line insertion, metastasis interventional therapy, resection of primary tumor, or elective surgery, will not be considered serious adverse events.
- Results in persistent or significant disability/incapacity
- Is a congenital anomaly or birth defect
- Is an important medical event (defined as a medical event(s) that may not be immediately life-threatening or result in death or hospitalization but, based upon appropriate medical and scientific judgment, may jeopardize the subject or may require intervention (e.g., medical, surgical) to prevent one of the other serious outcomes listed in the definition above). Examples of such events include, but are not limited to, intensive treatment in an emergency room or at home for allergic bronchospasm; blood dyscrasias or convulsions not resulting in hospitalization; or the development of drug dependency or drug abuse.
 - Potential drug induced liver injury (DILI) is also considered an important medical event.
 - Suspected transmission of an infectious agent (e.g., pathogenic or nonpathogenic) via the study drug is an SAE.

- Although pregnancy is not always serious by regulatory definition, it must be handled as an SAE.
- Ramucirumab and/or nivolumab overdose. For purposes of this trial, an overdose will be defined as any dose exceeding the prescribed dose for ramucirumab and/or nivolumab by 20%.
- Any venous or arterial event leading to discontinuation of ramucirumab therapy will be considered serious and should be reported per SAE guidelines.
- Cases of RPLS must be reported per SAE guidelines.

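### Section 5.3.3 bars any ramucirumab dose modification, while Table 2 in Section 6.3.1 orders reductions to 6 and then 5 mg/kg after proteinuria, and nothing says which prevails

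*Combined protocol and SAP*

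**What the plan says.** Section 5.3.3 fixes the dose: "Ramucirumab will be administered as a 60-minute intravenous infusion dosed at 8 mg/kg". It then requires recalculation when weight has changed by more than 10%, asks for rounding to whole milligrams, and closes with "There will be no dose modifications allowed". It states no exception and does not point to Section 6.

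Section 6.3.1 is headed as the section on ramucirumab dose modifications. The proteinuria row of its Table 2 applies from 2 g/24 h: treatment is held and may resume once the level is below 2 g/24 h. The dose column reads "Reduce dose to 6 mg/kg per dose for the first occurrence" and then "Reduce dose to 5 mg/kg for the second occurrence". Ramucirumab stops permanently for a third episode, for failure to fall below 2 g/24 h within 2 weeks, for a level above 3 g/24 h, or for nephrotic syndrome.

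Two other sections touch the point. For proteinuria, Section 5.4.1 says: "For guidelines on treatment holds, timing for restarting treatment or discontinuing treatment permanently, see Section 6.2.1, Table 2". Section 10.1.4 repeats the weight and rounding instructions of 5.3.3 without the ban.

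**The concern.** The two sections govern the same drug in the same subject at the same moment, the restart after a proteinuria hold, and they give different doses. A pharmacist or investigator working from the administration section restarts at 8 mg/kg, although the safety table lowers the dose. A site working from Table 2 gives a dose that 5.3.3 forbids.

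Section 10.1.5 names proteinuria/nephrotic syndrome as an important identified risk of ramucirumab, and the lower restart dose is part of the protocol's response to it. Whichever rule a site follows, the other gives grounds for recording a protocol deviation, and deviations are among the items the DSMB reviews (Section 13.1). Section 11.1.3 adds a further consequence: "an overdose will be defined as any dose exceeding the prescribed dose for ramucirumab and/or nivolumab by 20" percent, and an overdose is handled as a serious adverse event. Whether an 8 mg/kg restart falls under that definition depends on which section sets the prescribed dose.

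**Working it through.** **1. The sections side by side**

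| Section | What it says on restart dose after a proteinuria hold | Settles the conflict? |
|---|---|---|
| 5.3.3 | 8 mg/kg; no modification; no exception | No |
| 6.3.1, Table 2 | 6 mg/kg, then 5 mg/kg | No; does not mention 5.3.3 |
| 5.4.1 | Sends the site to Table 2 for holds, restart timing and discontinuation; dose not mentioned; cites Section 6.2.1, but Table 2 is in 6.3.1 | No |
| 6.1 and 6.2 | Length of delay, discontinuation, infusion reactions | No |
| 10.1.4 | Repeats the weight and rounding text; silent on reductions and on the ban | No |

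Proteinuria is the only Table 2 row that lowers the mg/kg dose. The other rows give no reduction or permanent discontinuation.

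**2. Size of the dose difference**

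Inputs: 8 mg/kg (5.3.3); 6 and 5 mg/kg (Table 2); 80 kg, the median weight quoted in Section 10.2.5 for nivolumab-treated patients.

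- Against the first reduction: 8/6 − 1 = 33.3%. At 80 kg: 640 − 480 = 160 mg per infusion.
- Against the second reduction: 8/5 − 1 = 60.0%. At 80 kg: 640 − 400 = 240 mg per infusion. This needs a second qualifying episode.

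**3. Overdose threshold, if Table 2 sets the prescribed dose**

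1.2 × 6 = 7.2 mg/kg and 1.2 × 5 = 6.0 mg/kg, so 8 mg/kg exceeds both. If 5.3.3 sets the prescribed dose, 8 mg/kg is simply the prescribed dose.

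**4. How often the question could arise**

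The documents give neither the share of subjects who reach 2 g/24 h (call it p) nor the share of those who may restart under Table 2 (call it q). Both are assumed here. With n = 35 (Section 12.3), the chance of at least one restart decision is 1 − (1 − pq)^35:

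| | p = 1% | p = 5% | p = 10% |
|---|---|---|---|
| q = 100% (upper bound) | 30% | 83% | 97% |
| q = 75% | 23% | 74% | 93% |
| q = 50% | 16% | 59% | 83% |
| q = 25% | 8% | 36% | 59% |

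For example, with p = 5% and q = 50%: 1 − (1 − 0.025)^35 = 0.588. The expected number of such subjects at q = 50% is 35 × p × 0.5, which is 0.175, 0.875 and 1.75 for the three values of p. These are chances that a site faces the choice, not chances that a wrong dose is given.

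**The case against.** The best defence is that 5.3.3 was never meant to be read literally. Its last sentence closes a paragraph on weight and rounding that itself orders recalculation, and the protocol uses the term dose modification for holds and discontinuations too, which nobody would think 5.3.3 forbids. On this reading the sentence bars only ad hoc changes, and toxicity is left to Section 6. The specific rule would normally override the general one. A site sent to Table 2 by 5.4.1 for restart timing will see the reduced dose in the next column, and the wrong section number does little harm because there is only one Table 2. Table 2 is also titled as guidelines, the subjects affected are few, the overdose and deviation consequences are conditional, and the probabilities above span too wide a range to say much.

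Much of this is fair. It makes Table 2 the probable intent, and only the dose comparison in step 2 follows from the documents without assumptions. But the milder reading is an inference. Recalculating for weight leaves the mg/kg level at 8, so it does not show that 5.3.3 tolerates a lower level. The Table 2 cells are worded as instructions, whatever the table's title. A site should not have to work out a safety dose by deciding which section its authors meant to prevail.

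**Conclusion.** The contradiction is real and unresolved in the text. Followed as written, 5.3.3 produces a restart dose one third above the safety table's first level, or 60% above its second. It concerns only subjects who reach 2 g/24 h without exceeding 3 g/24 h or developing nephrotic syndrome and who recover within 2 weeks, at a first or second episode. How many of the 35 that will be cannot be known from the documents. That an 8 mg/kg restart would count as an overdose rests on taking Table 2 as the prescribed dose. The sample size and the analysis of response rate are not affected. This should be corrected because it concerns safety dosing, the likely intent is clear, and the correction is small.

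**What to change.** Replace the last sentence of Section 5.3.3 with: *No dose modifications are allowed other than the proteinuria reductions in Section 6.3.1, Table 2.* This covers the only Table 2 row that lowers the mg/kg dose. It leaves intact the weight recalculation ordered in the same paragraph, which keeps the mg/kg level, and the holds and discontinuations in Table 2. While the text is open, the pointers in Section 5.4.1 could be corrected from 6.2.1 to 6.3.1; that is helpful but not needed to remove the conflict. The cost is one sentence, with no new test, visit or data item.

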5.3.4. Monitoring

- Vital signs including blood pressure, pulse, temperature, respirations, and pulse oximetry, will be measured as follows:
 - for the first two cycles of the nivolumab infusion: before, 5 min after start of the infusion, and 30 min (\pm 5 min) after the end of the infusion;
 - if vital signs are stable for first two cycles, subsequent cycles: before and 5 min (\pm 5 min) after the end of the infusion
 - Ramucirumab infusion: before the infusion, 30 min (\pm 5 min) after the start of the infusion, and after (\pm 5 min) the end of the infusion
- Subjects will be closely monitored for toxicities. Toxicity will be assessed using CTCAE version 4.

5.3.5 Dose Delay Due to Toxicity

If both drugs are held on Day 1 due to toxicity, the day treatment is resumed will be considered Day 1 of the cycle. If only one drug is held on Day 1 due to toxicity, the dose of that drug will not be made up.

5.4. Supportive Care

Subjects should receive appropriate supportive care measures as deemed necessary by the treating investigator. Suggested supportive care measures for the management of adverse events that are related to ramucirumab and nivolumab are outlined below. Where appropriate, these guidelines include the use of oral or intravenous treatment with corticosteroids as well as additional anti-inflammatory agents if symptoms do not improve with administration of corticosteroids. Note that several courses of steroid tapering may be necessary as symptoms may worsen when the steroid dose is decreased. For each disorder, attempts should be made to rule out other causes such as metastatic disease or bacterial or viral infection, which might require additional supportive care. The treatment guidelines are intended to be applied when the investigator determines the events to be related to ramucirumab or nivolumab.

5.4.1. Suggested supportive care measures for the management of adverse events that are related to ramucirumab

Infusion-Related Reactions

- Signs and symptoms usually develop during or shortly after drug infusion and generally resolve completely within 24 hours of completion of infusion.
- For guidelines on treatment holds, timing for restarting treatment or discontinuing treatment permanently, see Section 6.2.1, Table 2.

Proteinuria

- Treat proteinuria according to established guidelines.
- For guidelines on treatment holds, timing for restarting treatment or discontinuing treatment permanently, see Section 6.2.1, Table 2.

Hypertension

- Treat hypertension according to established guidelines.
- For guidelines on treatment holds, timing for restarting treatment or discontinuing treatment permanently, see Section 6.2.1, Table 2.

Wound Healing

- Treat wound according to established guidelines.
- For guidelines on treatment holds, timing for restarting treatment or discontinuing treatment permanently, see Section 6.2.1, Table 2.

Reversible Posterior Leukoencephalopathy Syndrome (RPLS)

- Treat RPLS according to established guidelines.
- For guidelines on treatment holds, timing for restarting treatment or discontinuing treatment permanently, see Section 6.2.1, Table 2.

Arterial Thrombotic Events

- Initiate anticoagulation therapy.
- For guidelines on treatment holds, timing for restarting treatment or discontinuing treatment permanently, see Section 6.2.1, Table 2.

Pulmonary Embolism (PE) or Venous thromboembolism (VTE)

- Initiate anticoagulation therapy.
- For guidelines on treatment holds, timing for restarting treatment or discontinuing treatment permanently, see Section 6.2.1, Table 2.

Gastrointestinal Perforation or Fistula Formation

- Initiate treatment according to established guidelines.
- For guidelines on treatment holds, timing for restarting treatment or discontinuing treatment permanently, see Section 6.2.1, Table 2.

Bleeding

- Initiate treatment according to established guidelines.
- For guidelines on treatment holds, timing for restarting treatment or discontinuing treatment permanently, see Section 6.2.1, Table 2.

Hepatic Encephalopathy or Other Serious Signs of Liver Impairment

- Initiate treatment according to established guidelines.
- For guidelines on treatment holds, timing for restarting treatment or discontinuing treatment permanently, see Section 6.2.1, Table 2.

5.4.2. Suggested supportive care measures for the management of adverse events that are related to nivolumab

Immuno-oncology (I-O) agents are associated with AEs that can differ in severity and duration than AEs caused by other therapeutic classes. Nivolumab is considered an immuno-oncology agent in this protocol. Early recognition and management of AEs associated with immuno-oncology agents may mitigate severe toxicity. Management algorithms have been developed to assist investigators in assessing and managing the following groups of AEs: Gastrointestinal, Renal, Pulmonary, Hepatic, Endocrinopathies, Skin, Neurological.

For subjects expected to require more than 4 weeks of corticosteroids or other immunosuppressants to manage an AE, consider recommendations provided in the algorithms. These algorithms are found in the Nivolumab IB and in Appendix 1. The guidance provided in these algorithms should not replace the Investigator's medical judgment but should complement it.

